## **9. Research methods**

### **9.1 Study design**

This will be a retrospective cohort study to describe patient characteristics and incidence of hypothyroidism in a pediatric population of children up to 365 days after a diagnostic scan with iodinated contrast agent. The study will be based on secondary data collection only.

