#### **9.2.3 Study population**

The study population will be all patients who were under the age of 4 at some time during the years 2008 to 2015 in the US- based KPNC database who had a procedure with iodinated contrast agent. A preliminary search of the data identified around 2300 people under age 4 who had a procedure with iodinated contrast, by searching CPT and HCPCS codes. We will also require that all children in the study were members of KPNC for at least 3 months before the iodinated contrast exposure, except where the child is under 3 months of age at time of initial exposure, and 2 weeks after the exposure. From this population we will exclude all children who had a diagnosis of hypothyroid any time prior to the iodine contrast exposure. We will also exclude those with lab values for low thyroid (TSH > 5 mU/L for children) any time before the

exposure, and those with thyroid replacement therapy, Hashimoto thyroiditis, or congenital hypothyroidism any time prior to the exposure.

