## **9.3 Variables**

### **9.3.1 Baseline characteristics**

- Demographics characteristics (age, sex, year of procedure)
- Clinical characteristics (comorbidities, type of radiological examination, bodyweight, height, head-circumference, laboratory values (TSH, T3, T4 anti-thyroid antibodies, if available), and co-medications.

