### **9.3.3 Outcome measures**

Potential cases of hypothyroidism will be defined by:

- A coded diagnosis of hypothyroidism and/or
- A thyroid function tests indicating hypothyroidism and/or
- New use of thyroid replacement therapy

Cases of hypothyroid will be identified using ICD 9 DM codes, lab values and NDC codes. See appendix for code lists. From the exposed population we will identify all children who have a diagnosis of hypothyroidism in the 365 days after iodine contrast exposure. We will also identify those with lab values for low thyroid (TSH > 5.0 mU/L) or receipt of thyroid

replacement therapy in the 365 days post exposure. All children who meet any of these criteria will be considered potential cases of hypothyroidism. We will review the electronic record of each child considered to be a potential case to confirm that they did not have hypothyroidism prior to exposure to the iodine contrast agent. We will also look for codes that support the presence of the hypothyroid condition. For example if a child receives more than one prescription for thyroid replacement, or has multiple labs with high TSH levels, or multiple codes for hypothyroidism these will be considered likely cases. We will then obtain original clinical notes to validate the diagnosis, by searching for evidence of pre-existing thyroid conditions. Specifically will look for a positive diagnosis of hypothyroid, lab results, repeated lab tests, notes of other medications associated with lowered thyroid (see appendix 3 for list of drugs), and of Hashimoto thyroiditis, radiation, surgical procedures (see appendix 3 for list of procedures), and congenital forms of hypothyroid.

After review of their electronic medical record, detected cases will be classified into:

- Probable iodine-induced hypothyroidism: no other cause than the previous iodine contrast medium exposure could be identified
- Possible alternative etiology: Known other diseases (e.g. Hashimoto thyroiditis) or treatments (e.g. radiotherapy, drug treatments such as TK inhibitors, interferons, amiodarone and others) which may cause hypothyroidism
- Not a hypothyroidism case: No evidence of hypothyroidism in the patient's medical record, e.g. coding error

Estimated incidence rates will be calculated for all hypothyroidism cases together, and separate for "possible iodine induced hypothyroidism" and "possible alternative etiology."

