## **9.4 Data sources**

KPNC is an integrated health care delivery system providing health care to over 3.8 million members with 3,300 physicians, 32 outpatient clinics and 17 hospitals. Analysis of U.S. census data demonstrates that KPNC members are representative of the population living in the served geographic area. KPNC maintains medical information on each patient through a computerized

EHR database called “Health Connect” since 2007. Therefore, we have access to high quality clinical data.

Admitting, Discharge and Transfer (ADT) System. A complete database on all hospitalizations at any KPNC hospital since 1971 is maintained with data that are highly comparable to the UB-92 forms (required of all hospitals in California and most other States), and contains a principal and up to 12 secondary discharge diagnoses and codes for up to seven procedures for each hospitalization. Admitting and discharge diagnoses and procedures are coded according to the International Classification of Disease, 9th revision (ICD-9). The accuracy of principal discharge diagnoses obtained from Kaiser Permanente databases has been verified in other studies.

The Laboratory Utilization and Reporting System (LURS) is a clinical database that captures all laboratory tests and results performed at the Kaiser Permanente of Northern California regional laboratory since 1991. In 1995, LURS incorporated all hospital-based laboratories of Northern California. Providers use this system to order tests, obtain results and share them with patients. Thus, data in LURS are of higher quality than a chart review study could achieve (since chart review involves small rates of reviewer and transcription error). LURS contains patient name, medical record number, test name (each test has a unique code), date, and result. Essentially all thyroid tests ordered are available in the LURS database.

Outpatient Service Clinical Record (OSCR), a computerized database, will be a source to identify outpatient diagnosis of thyroid disorders.

The database contains a unique identifier for all information on all drugs issued to patients, all hospitalizations, captured with ICD-9 coding, outpatient diagnoses and laboratory tests and result. KPNC membership is stable and more than 97% of members have 5 or more years of membership.

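### The pre-exposure TSH exclusion acts only on tested children, so raised TSH first detected after contrast can be classed by default as new, probable iodine-induced hypothyroidism

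*Combined protocol and SAP*

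**What the plan says.** **Entry (9.2.3).** On diagnosis, "we will exclude all children who had a diagnosis of hypothyroid any time prior to the iodine contrast exposure". On laboratory values, "We will also exclude those with lab values for low thyroid (TSH > 5 mU/L for children) any time before the" exposure. Prior thyroid replacement, Hashimoto thyroiditis and congenital hypothyroidism also exclude. Children must have been "members of KPNC for at least 3 months before the iodinated contrast exposure, except where the child is under 3 months of age" at first exposure. No pre-exposure TSH is required.

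**Data (9.1, 9.3.1, 9.4).** "The study will be based on secondary data collection only", so the study cannot add a test. Baseline variables include "laboratory values (TSH, T3, T4 anti-thyroid antibodies, if available". On the laboratory system, 9.4 says "Essentially all thyroid tests ordered are available in the LURS database".

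**Outcome (9.3.3).** A coded diagnosis within 365 days makes a potential case. So does a raised TSH or treatment: "We will also identify those with lab values for low thyroid (TSH > 5.0 mU/L) or receipt of thyroid" replacement. No comparison with a pre-exposure value is asked for. Each potential case then has the electronic record reviewed "to confirm that they did not have hypothyroidism prior to exposure to the iodine contrast agent", and clinical notes are searched for earlier thyroid disease and other causes. A confirmed case with no cause other than contrast goes to the probable iodine-induced class. A known disease or treatment that could explain it sends it to possible alternative etiology.

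**Limitations (9.9).** Undiagnosed hypothyroidism is mentioned only as cases the study will fail to count.

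**The concern.** A child can pass the TSH screen in two ways: by having been tested without a raised value, or by never having been tested. The visible text treats these as one state. Only in the first is there evidence that thyroid function was normal at some time before contrast. In the second, a raised TSH found after the procedure may be new or may be old and newly found, and the classification does not separate the two.

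This differs from the length of look-back. A child enrolled since birth and never tested has no more TSH values than one enrolled for three months, so longer membership would not close the gap.

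What is at stake is mainly the probable iodine-induced rate, which a reader will take as onset after contrast. Two secondary descriptions are also exposed. For a child whose disease predates the procedure, the time from contrast to diagnosis is only the time to first detection, and the episode's duration is counted from the wrong start.

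**Working it through.** The plan has no figure to reproduce: the study size is a database count, with no expected rate or target precision. The check is therefore a trace through the rules, followed by an illustration of size.

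**Trace: a child never tested, TSH already above 5 mU/L, no diagnosis or treatment on record.**

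1. Entry (9.2.3): no diagnosis, laboratory value or therapy is recorded, so no exclusion applies and the child enters.
2. Follow-up (9.3.3): if no test, diagnosis or treatment occurs within 365 days, the child is never a potential case. This is the situation 9.9 describes.
3. If a TSH is drawn and exceeds 5.0 mU/L, the child becomes a potential case.
4. Review (9.3.3): notes may show earlier thyroid disease, a congenital form, Hashimoto thyroiditis, a relevant drug, radiation or surgery. The child is then removed or reclassified. Repeat tests may also show that a raised value was isolated.
5. If the record is silent on all of these and the raised TSH persists, nothing contradicts onset after contrast. Repeat raised values confirm disease, not its starting date. The child falls into the probable iodine-induced class.

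A child with a documented normal TSH before contrast and a raised one afterwards ends in the same class. The two are indistinguishable in the resulting rate.

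**Illustration of size.** Expected number of such children = N × u × p × q × r, where

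- N = 2300 (9.2.3 and 9.5; a count before exclusions);
- u = share untested before exposure, assumed 50% to 90%;
- p = prevalence of an unrecorded raised TSH among them, assumed 0.5% to 3%;
- q = chance of a TSH test within 365 days, assumed 5% to 30%;
- r = share that review cannot recognise as pre-existing or otherwise caused, assumed 50% to 100%.

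The documents give none of u, p, q or r.

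- Low: 2300 × 0.50 × 0.005 × 0.05 × 0.50 = 0.14
- Middle: 2300 × 0.90 × 0.01 × 0.10 × 1.00 = 2.07
- High: 2300 × 0.90 × 0.03 × 0.30 × 1.00 = 18.63

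If each child contributes at most one year, person-time is at most 2300 years. The added rate is then 0.14/2300 = 0.06, 2.07/2300 = 0.9 and 18.63/2300 = 8.1 per 1000 person-years.

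**Relative effect.** With k observed probable cases, s of them pre-existing, the rate is inflated by k/(k − s):

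- k = 10: s = 2 gives 10/8 = 1.25; s = 5 gives 10/5 = 2.0
- k = 20: s = 2 gives 20/18 = 1.11; s = 5 gives 20/15 = 1.33
- k = 50: s = 2 gives 50/48 = 1.04; s = 5 gives 50/45 = 1.11

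The relative effect thus depends on a case count that the documents do not supply.

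**The case against.** **Review already guards against this.** A reader might infer that every untested child with a raised TSH is counted as a probable case. The documents do not support that. The child must first be tested, diagnosed or treated within 365 days, and a raised value makes only a potential case. Section 9.3.3 then requires record and note review with three possible outcomes, and 9.8 adds abstraction from the complete medical record. This narrows the problem to children whose record is silent. For those, it has no answer.

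**The objective concerns detection.** Section 8.1 speaks of hypothyroidism found in routine practice, and no rise from baseline is promised. That softens the point for the overall rate. It does not rescue the probable class: the plan excludes prior disease, confirms its absence and attributes cases to iodine, all of which presuppose onset after exposure.

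**Baseline laboratory values will be described anyway.** Sections 8.2 and 9.7 describe baseline characteristics for cases, by category, and for the rest of the cohort. That could show how many had a TSH, but it neither alters the label nor gives a rate by baseline status. Text at the end of 9.7 is blacked out and the Annex 2 checklist says stratified analyses are included, so it cannot be said that no such split was planned. The label in 9.3.3 and the silence in 9.9 are visible either way.

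**The effect may be trivial.** The one incidence quoted for term neonates in section 7, 8.3%, would give 2300 × 0.083 = 190.9 cases, against which 2.07 is about 1%. That figure covers neonates only and comes from studies described as heavily biased, so it does not settle the matter. It does show that any headline percentage is driven by the chosen denominator.

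**Strata would not be comparable.** Children tested beforehand may differ in morbidity and later testing. This stands, and limits how the split may be used.

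**Conclusion.** The point holds in a conditional form. A never-tested child with an already raised TSH can enter the cohort. If disease is first detected within 365 days and review finds no earlier disease or other cause, the child is classed by default as incident and probable iodine-induced. The plan's stated limitations do not cover this.

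This mechanism can only add cases, mainly to the probable rate. Its size is open: from under 1 to over 10 children in about 2300, on assumed values of all four inputs.

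Three stronger readings are not supported:

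- **That the reported rate is too high on balance.** Undiagnosed cases missed during follow-up act the other way, so the net direction is not established.
- **That a percentage inflation can be quoted.** It needs a true case count that the documents do not give.
- **That excluding a child on any single earlier raised TSH is also an error.** It is a defensible, conservative rule for an incident-case cohort.

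The change is worth making because it is cheap and is the direct way to show how much of the probable rate rests on a known baseline.

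**What to change.** - **9.3.1:** derive from LURS a baseline thyroid status for every child: last pre-exposure TSH at or below the plan's cut-off, or never tested.
- **9.3.3:** flag any case without a pre-exposure value as baseline unknown. The etiology classes can stay as they are.
- **9.7:** report cases, person-time and rate by baseline status, and the probable iodine-induced rate with and without baseline-unknown cases. Present this as a sensitivity analysis, not as a comparison between strata. If the blacked-out text already contains such a split, a cross-reference suffices.
- **9.9:** state that disease present but unmeasured before contrast may be counted as new, alongside the existing statement on missed cases.

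Cost: one derived variable, a few table rows and a sentence, all from data already held, with no change to the cohort or cut-off. The documented-normal stratum will probably be small with a wide interval, and its children may differ from those never tested, so its rate should not be read as the bias-free answer for the whole cohort.

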## **9.3 Variables**

### **9.3.1 Baseline characteristics**

- Demographics characteristics (age, sex, year of procedure)
- Clinical characteristics (comorbidities, type of radiological examination, bodyweight, height, head-circumference, laboratory values (TSH, T3, T4 anti-thyroid antibodies, if available), and co-medications.

### **9.3.2 Exposure**

Exposure will be identified through CPT codes for procedures that include iodinated contrast agent. The date the procedure was coded will be considered the date of exposure. The majority of these will be CT scans with contrast. We will also identify young children who had a left heart catheterization including cardio-angiography, ventriculography, and coronary angiography. Each child will be followed for up to 365 days after a qualifying exposure (the exposure window).

There will be no differentiation according to any specific brand of contrast agents, considering that there is general agreement that iodine induced hypothyroidism is considered a class-effect of all iodinated contrast agents and not restricted to specific agents

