## **9.9 Limitations of the research methods**

There is access to original clinical records in the KPNC database, thus validation will be possible. However we may miss some children who had procedure using iodinated contrast if the procedures were not coded properly. It is also possible that some children will have undiagnosed hypothyroidism. These will also be missed in this study.

Although most members enroll through their employers, many are members of KPNC through MediCal (a low-income health insurance plan). Analysis of U.S. census data demonstrates that KPNC members are representative of the general population with regard to ethnicity and education and differ only slightly with regard to income, we tend to underrepresent the very rich and the very poor. Members are remarkably similar to the general population in terms of employment status, marital status, screening practices, and prevalence of medical conditions, when compared with population-based data from the California Behavioral Risk Factor Surveillance System.

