### Annex 3. Additional information

#### *Codes for procedures used to identify study patients exposed to iodinated contrast agents*

Procedure codes	CPT and HCPCS	Data source
CT scans with contrast	70470, 70482, 70488, 70491, 70492, 70496, 70498, 71270, 71275, 72126, 72127, 72128, 72129, 72130, 72133, 72191, 72194, 73202, 73206, 73702, 73706, 74170, 74174, 74175,	KPNC data
Left heart catheterization	93452, 93453, 93454, 93455, 93456, 93457	
Ventriculography	93458, 93459, 93460, 93461	
Cardio/ Coronary angiography	93563, 93564, 93565, 93566	

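### Exposure is found by CPT/HCPCS codes only, while the one hospital procedure file the protocol describes is coded in ICD-9, so correctly coded inpatient contrast procedures could be missed

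*Combined protocol and SAP*

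**What the plan says.** Three places define how exposed children are found, and all use the same code systems.

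- Section 9.3.2: "Exposure will be identified through CPT codes for procedures that include iodinated contrast agent". It adds: "We will also identify young children who had a left heart catheterization including cardio-angiography, ventriculography, and coronary angiography".
- Section 9.2.3: "A preliminary search of the data identified around 2300 people under age 4 who had a procedure with iodinated contrast, by searching CPT and HCPCS".
- Annex 3, exposure table: the only code column is CPT and HCPCS. The heart procedures are listed in the same way, for example "93452, 93453, 93454, 93455, 93456, 93457" for left heart catheterization. The data source is given only as KPNC data.

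Section 9.4 describes the files. The hospital admission, discharge and transfer system is presented as a complete record of KPNC hospital stays, with "codes for up to seven procedures for each hospitalization". On coding it says: "Admitting and discharge diagnoses and procedures are coded according to the International Classification of Disease, 9th revision (ICD-9"). The other named files are a laboratory system, an outpatient record cited as a source of thyroid diagnoses, and the HealthConnect electronic record, in use since 2007, whose procedure coding is not described.

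On missed exposure, section 9.9 says only: "However we may miss some children who had procedure using iodinated contrast if the procedures were not coded properly".

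**The concern.** The search uses one coding language, and the only file described as holding hospital procedures uses another. The protocol lists no ICD-9 procedure codes for contrast CT or cardiac angiography, gives no crosswalk, and does not say which KPNC files the search covers. A child whose only contrast procedure was done in hospital and recorded only in ICD-9 would not enter the cohort, even with faultless coding. That is a different problem from the one section 9.9 concedes.

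The composition of the cohort is at stake, and through it the primary incidence rate. Section 7 describes neonates as especially susceptible and cites a review in which 8.3% of term and 18.3% of premature infants developed hypothyroidism after contrast. That such infants are often inpatients when exposed is an inference, not a statement in the protocol. If it is right, a gap in inpatient capture would fall on the group that matters most.

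**Working it through.** **Step 1. Is there a mismatch?** Yes, on the text. Sections 9.2.3 and 9.3.2 and Annex 3 use CPT or CPT/HCPCS; section 9.4 gives ICD-9 for hospital procedures. No sentence connects the two. The protocol is not confined to CPT elsewhere: the Annex 3 table of drugs and procedures associated with hypothyroidism has a combined ICD-9-CM, CPT and NDC column, with one code filled in (92.2, neck irradiation).

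**Step 2. Would a planned check find a missed exposure?**

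- Section 9.8 samples records to confirm that the study population meets the criteria. This can find children wrongly included, not children left out.
- Section 9.8 also cross-tabulates the study population by characteristics such as age, sex and comorbidities. Care setting is not mentioned, and the tables contain only selected children.
- Section 9.3.3 reviews the records of potential cases within the exposed population.

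All three act after selection. The Annex 2 checklist marks selection bias as not applicable.

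**Step 3. Can the stated figure be reproduced?** No. The figure of about 2300 is a database count without formula or inputs, and it came from the CPT/HCPCS search itself. It therefore cannot show whether that search is complete.

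**Step 4. What could a gap do?** Let *f* be the share of exposed children with no CPT/HCPCS-coded contrast procedure. The documents do not give *f*; the values below are assumptions that show the mechanism, not estimates.

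Exposed children in total = 2300 / (1 − *f*):

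- *f* = 5%: 2300 / 0.95 = 2421, about 121 missed
- *f* = 10%: 2300 / 0.90 = 2556, about 256 missed
- *f* = 20%: 2300 / 0.80 = 2875, 575 missed

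Missed children leave both numerator and denominator. Treating the one-year rate as a risk for simplicity, overall risk = (1 − *f*) × captured risk + *f* × missed risk. Captured risk is assumed; missed risk is either equal to it or one of the two figures cited in section 7.

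| *f* | Captured risk | Missed risk | Overall risk | Reported / overall |
|---|---|---|---|---|
| 10% | 1% | 1% | 0.9 + 0.10 = 1.00% | 100% |
| 10% | 1% | 8.3% | 0.9 + 0.83 = 1.73% | 58% |
| 10% | 1% | 18.3% | 0.9 + 1.83 = 2.73% | 37% |
| 20% | 1% | 8.3% | 0.8 + 1.66 = 2.46% | 41% |
| 10% | 2% | 8.3% | 1.8 + 0.83 = 2.63% | 76% |

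The first row is as important as the others: with equal risk there is no bias, only a smaller cohort. The rows with 8.3% or 18.3% are extreme, because they give every missed child a neonatal risk in a cohort that runs to age 4.

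**Step 5. A second route.** A child with a missed inpatient exposure and a later CPT-coded scan would get the later date as index date. A TSH above 5 mU/L or a hypothyroidism diagnosis between the two would then trigger the prior-disease exclusion in section 9.2.3, and a case following contrast would be removed.

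**The case against.** The strongest objection is that the gap exists only if inpatient contrast procedures lack a CPT record, and the protocol never says they do. HealthConnect covers the whole study period and may hold inpatient CPT codes. Annex 3 gives the source as KPNC data, not an outpatient file. The authors also target heart catheterization with CPT codes, which suggests that they expect to retrieve it that way. This stands: no missed child is shown. It does not settle the matter, because the protocol does not say which files the search covers or that any of them carries inpatient CPT codes.

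It can also be said that ICD-9 codes may not show whether contrast was given, and that the limit of seven per stay may drop some procedures. Both points are fair, and they affect how the fix is built.

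A reader might go further in four ways that the documents do not support.

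- **That the CT list is itself wrong.** The uneven run "72126, 72127, 72128, 72129, 72130, 72133" might suggest that a non-contrast code is included or that contrast codes are left out. Annex 3 prints numbers without descriptors, and the CT list ends on a comma, so it may be cut short in the text available. Nothing can be concluded.
- **That cardiac patients are a named high-risk group.** Section 7 singles out neonates and preterm infants only. Heart catheterization matters here because it is an intended exposure.
- **That the rate is biased downwards.** This requires the missed children to be at higher risk. It is plausible, but not established. Section 7 also reports that the studies behind its neonatal figures were strongly affected by bias.
- **That a missed fraction can be estimated.** The documents give no inpatient share. A guessed share of procedures could not be applied to 2300 children in any case, since a child with several procedures is captured if any one has a listed code.

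**Conclusion.** The concern holds as a possible under-capture of inpatient exposures that the plan neither rules out, checks for, nor acknowledges. Its size is unknown. It rests on one assumption the documents leave open: that some inpatient contrast procedures have no CPT/HCPCS record in the files searched. If the missed children are disproportionately neonates or preterm infants, the incidence rate would be too low. If their risk matches that of the captured children, leaving them out costs precision only. Because this decides who enters the cohort and is inexpensive to resolve, it should be dealt with before the cohort is extracted.

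**What to change.** 1. In section 9.3.2, state which KPNC files are searched and whether they include inpatient procedures.
2. Define exposure as the union of the listed CPT/HCPCS codes and ICD-9 procedure codes for contrast CT and cardiac catheterization or angiography in the hospitalization file. Where an ICD-9 code does not show contrast use, supplement it with HealthConnect procedure records. Add the codes to Annex 3 and take the earliest qualifying exposure across sources as the index date.
3. Re-run the count of about 2300 by inpatient or outpatient setting and by age, with neonates shown separately, and report how many children each source adds. If the ICD-9 and HealthConnect search adds almost none, that answers the concern.
4. Extend section 9.9 to any remaining inpatient under-capture, including the limit of seven procedures per stay, and to its possible effect on the rate.

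The cost is a longer code list and a repeat of the preliminary search, plus some record checking where contrast use is unclear. No new data collection is needed: section 9.6 already builds a data set of all children under 4 before exposed children are picked out. The work has to fit the October to November 2016 data-collection window in section 6.
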